A sample size of 32 participants was calculated to be sufficient for a two-tailed significance level of 5% and a power of 80% (Appendix A). This was adjusted to 45 participants with knee osteoarthritis to allow for dropouts. Recruitment for this study will be conducted using a recruitment flyer and through the CIONIC website. Recruitment will be based on a first come

basis. Interested participants will complete a questionnaire to be reviewed according to the inclusion and exclusion criteria. Responses will then be reviewed, and prospective participants will be invited to schedule a virtual meeting with a study staff member who will screen the prospective subject for an understanding of the study and for their voluntary participation. All participants will be assigned a unique number using a computer random number generator and randomly assigned to a group by a researcher. All participants will receive their assigned intervention at their first lab visit.

Inclusion Criteria

- Persons with knee osteoarthritis between the ages of 22 and 75
- Ability to walk a duration of 30 minutes per walking session (with or without an assistive device), for three days per week
- Able to tolerate the device for up to 1 hour per lab session
- No recent change in medication or exacerbation of symptoms over the last 60 days
- Radiographic KOA K&L grade 2 or 3 or physician diagnosed mild or moderate KOA if radiographic imaging is not available
- No hyaluronic acid or cortisone injection into knees in previous 12 months

Exclusion Criteria

- Lower motor neuron disease or injury (e.g. peripheral neuropathy) that may impair response to stimulation
- Absent sensation in the impacted or more impacted leg

- Inadequate response to stimulation, as defined as inability to achieve muscle contraction or tolerate stimulation
- Inability to ambulate with the sleeve in place of an ankle foot orthosis (AFO)/knee ankle foot orthosis (KAFO) if utilized
- Use of FES devices in the past year
- Demand-type cardiac pacemaker or defibrillator
- Malignant tumor in the impacted or more impacted leg
- Existing thrombosis in the impacted or more impacted leg
- Fracture or dislocation in the impacted or more impacted leg that could be adversely affected by motion from stimulation
- History of knee surgery
- History of other types of arthritis
- History of neurological disease
- History of seizures or diagnosed with epilepsy/seizures
- Current pregnancy

Methodology

Overview of Study

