This study is a randomized controlled trial. Figure 2 depicts a flow diagram of the study design. Participants will be screened for eligibility through a questionnaire, and after study details are explained and consent is obtained, they will be invited to the study site. Assessments will be conducted at CIONIC Inc., and involve approximately 45 patients for a 12 week study period.

CIONIC

CIONC FOR ORTHOPEDICS

All subjects will be assigned an electrical stimulation system to wear on the most impacted leg and be prescribed a home-based exercise and walking program. Subjects will be randomly assigned into three groups: (a) control; (b) NMES+; (c) NMES+FES. The control group will not receive stimulation for the exercise and walking program, whereas subjects in NMES+ will receive stimulation during exercises, and subjects in the NMES+FES group will receive stimulation during exercises and walking. Outcome measures will be assessed at baseline, 6 weeks after baseline, and end of study (Table 2). Equipment and additional feedback will be collected at the end of study. These three groups will be analyzed using several outcome measures. Primary outcome measures of the study are quadriceps strength, perceived functional capacity, self-reported pain, and walking performance. Secondary interest will be adherence to program, thigh muscle volume, functional ability of the lower limb, and quality of life. The CIONIC system will be used to track adherence (duration of sessions, frequency of use).

[figure not shown]

Figure 2: Study flow

Table 2: Study overview

Comparison Groups	Treatment Schedule	Timing and Outcome Measures
Control (unstimulated exercise and walking)	Exercise: 5x/week for 12 weeks Progression every 3 weeks	At baseline, midpoint and end of study: Quadriceps strength Perceived functional capacity Self-reported pain Walking performance Thigh muscle volume Functional ability of lower limb Quality of life EMG activity
NMES+ (NMES+exercise and unstimulated walking)	Walking: 10 min, 3x/week for 12 weeks Progression up to 30 min by end of study	Weekly: Adherence to program
NMES+FES (NMES+exercise and FES+walking)		

Participant Identification, Recruitment & Informed Consent

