Other information to be collected include date of birth, gender, ethnicity, height, weight, duration of condition, and type and dosage of medication.

Data Analysis/Statistical Analysis

For each of the primary and secondary measures, we will perform a Shapiro-Wilk test for normality to assess the assumption of normality. If the outcome variable is approximately normally distributed, a paired t-test will be used to statistically compare outcome metrics before and after the intervention within a condition. If the normality assumption is not met, the Wilcoxon signed rank test will be used as an alternative to the paired t-test for this statistical comparison. Bonferroni multiple hypothesis correction will be utilized for a corrected significance level.

To compare across conditions, an analysis of variance (ANOVA) test will be performed if the outcome variable is normally distributed. If the normality assumption is not met, the Kruskal Wallis test will be used as the non-parametric version of ANOVA. We may also employ a repeated measures ANOVA test for inclusion of all three timepoints.

Organizational Relationships

CIONIC works closely with Edge Analytics, a consulting firm who has been contracting for CIONIC for over two years. The firm is primarily responsible for algorithm development and statistical analyses of kinematic and EMG data. [name], [name], and [name] are employees of Edge Analytics who have been working closely with Cionic. [name] is a sub-investigator on this study.

Risk & Benefit Assessment

The Cionic Neural Sleeve has been tested extensively in previous studies. Across these prior studies, the Cionic Neural Sleeve has been evaluated for walking and exercise mode, approved for FDA 510k submission and its intended use in a simulated home environment, and for home usability with no adverse events.

However, any study of this kind comes with some known risks, that although rare, are associated with participation:

- Discomfort from the electrical stimulation
- Minor skin irritation at the sites of sensor/electrode pad placement
- Muscle fatigue from prolonged device use
- Anxiousness due to the anticipation of receiving an electrical stimulation
- Injury caused by unintended falls while using the Cionic Neural Sleeve
- Exposure to coronavirus disease 2019 (COVID-19) or other communicable disease

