Appendix A: Power Analysis

Power and Significance Level

[figure not shown]
These are set to standard,

Power = 0.8

Significance Level (alpha) = 0.05

Metric	Effect Size used in calculation	Required sample size when comparing participants' sessions (paired sample)	Required sample size when comparing group A to group B
WOMAC - Function bivariate	0.71 ²⁷	18	32
WOMAC - Pain bivariate	0.41 ²⁷	49	94
WOMAC - Function Standing/Walking bivariate	0.45 ²⁷	41	78

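### No named analysis uses the week-6 data of participants who miss week 12; a prespecified mixed model would, at little cost

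*Combined protocol and SAP*

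**What the plan says.** The Overview of Study sets out three arms ("Subjects will be randomly assigned into three groups") and three assessments: "Outcome measures will be assessed at baseline, 6 weeks after baseline, and end of study".

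The section Data Analysis/Statistical Analysis is the whole analysis plan. Within an arm, "a paired t-test will be used to statistically compare outcome metrics before and after the intervention within a condition", with the Wilcoxon signed rank test if normality fails. Across arms it names ANOVA, or Kruskal Wallis if normality fails, without naming the visit compared or any baseline covariate. It then adds: "We may also employ a repeated measures ANOVA test for inclusion of all three timepoints". The documents contain no mixed model, imputation, analysis population or rule for a missed visit.

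On attrition, Participation Selection and Randomization calculates 32 participants and continues: "This was adjusted to 45 participants with knee osteoarthritis to allow for dropouts". It gives no dropout rate. Study Withdrawal lets participants leave at any time. It also lets the team remove them for, among other reasons, a study-related injury, a need for other treatment, or not following the study plan.

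**The concern.** Each named method needs data that a dropout does not have. A paired before-and-after test needs both values. A 12-week ANOVA or Kruskal Wallis test needs week 12. Classical repeated measures ANOVA normally discards anyone without a full set of visits. So the plan pays for a full week-6 assessment and then, for everyone who leaves later, does not use it in any 12-week comparison.

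The completer comparison is safe if leaving has nothing to do with response. The removal reasons in Study Withdrawal are ways in which people doing badly could leave. Discomfort from stimulation, listed in the Risk & Benefit Assessment, can arise only in the arms that receive stimulation. If one arm loses more of its poor responders, its remaining participants look better than the arm as randomised. The randomised comparison is then distorted in a study whose second aim is statistical evidence of effect. Because the three-visit method is optional, the choice can also be made after the data are seen.

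**Working it through.** **1. The plan's own figure.** Appendix A uses "Significance Level (alpha) = 0.05", power 0.8 and, in the row "WOMAC - Function bivariate", an effect size of 0.71. For two independent groups:

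n per group = 2 × ((1.960 + 0.842) / 0.71)² = 2 × 15.57 = 31.1, rounded up to 32 (32.1 from the t distribution).

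The 32 reproduces, but as a number per group. The same row's 18 reproduces as a paired t-test (17.6).

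**2. The dropout allowance.** If 32 is taken as the trial total, as Participation Selection and Randomization does, the allowance is 45 − 32 = 13, and 13 / 45 = 28.9%. If 32 is per group, two groups need 64 and three need 96. Both exceed 45, so no allowance remains. That is a separate sample-size issue. Here 29% serves only as a plausible level of loss.

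**3. What each method does with a person seen at baseline and week 6 but not at week 12.**
- Paired t-test or Wilcoxon, baseline to end of study: excluded.
- ANOVA or Kruskal Wallis at end of study: excluded.
- Classical repeated measures ANOVA on three visits: normally excluded.
- Likelihood-based mixed model: included through week 6.

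**4. Size of the bias (illustrative).** All inputs in this step are assumptions: two arms of 15 (45 split equally), unit SD, correlation 0.7 between weeks 6 and 12 and 0.5 of each with baseline, no true effect. Dropout occurs after week 6 and is more likely with a poor change to week 6 (logistic slope 1 to 2). The likelihood estimate fits week 6 on arm and baseline in everyone (arm effect a) and week 12 on arm, baseline and week 6 in completers (arm coefficient b, week-6 coefficient c). The estimate is b + c × a.

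False benefit for the stimulated arm, in SD, by dropout in control / stimulated:
- 29% / 29%: about 0 for completers.
- 25% / 33%: 0.03 to 0.04 for baseline-adjusted completers (0.02 to 0.05 if the week-6 value itself drives dropout).
- 20% / 40%: 0.07 to 0.11 for baseline-adjusted completers; 0.11 to 0.16 for unadjusted change.
- Likelihood estimate: about 0 throughout.

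The plan's ANOVA has no baseline term. Unadjusted week-12 values at 20% / 40% give about 0.07 to 0.16 when the week-6 value drives dropout, and less when the change drives it. By symmetry, exchanging the two dropout rates reverses every sign.

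**5. With a true effect.** With 0.71 SD at week 12, correlations of 0.5 to 0.7 and one dropout rule on the week-6 value in both arms (about 32% to 37% lost), the control arm loses more poor responders. Completers then give 0.63 to 0.67 and the likelihood estimate 0.70 to 0.71. Here the benefit is understated.

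**6. Precision.** The likelihood estimate's standard error is 0% to 5% below that of baseline-adjusted completers. At 29% in each arm, for example, 1 − 0.370 / 0.384 = 3.6%. It is about 15% below that of an unadjusted 12-week ANOVA, and most of that gap comes from the baseline covariate.

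**The case against.** The strongest reply is that the documents do not show the problem will occur. They give no dropout rate and no reason to expect the stimulated arms to lose twice as many people. The eligibility criteria exclude people who cannot tolerate stimulation. Under Risk Mitigation Strategies participants control its intensity, and earlier home use in 17 subjects is reported without adverse events. With equal dropout the simulated between-arm bias vanishes. Even at 20% versus 40%, the adjusted bias of 0.07 to 0.11 SD is about 0.2 to 0.3 of a standard error near 0.38 (0.07 / 0.38 = 0.18; 0.11 / 0.38 = 0.29). All of this stands, and it limits the weight of the point.

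It also rules out some stronger readings that a reader might infer:
- That the plan expects 29% dropout. It only allows for dropouts, and 29% follows only if 32 is the trial total.
- That up to 13 people would contribute nothing. They are lost to 12-week comparisons, but a week-6 comparison could use those seen then. Anyone who leaves before week 6 is lost to the proposed model as well.
- That completer analysis must flatter stimulation. Step 5 shows the opposite.

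Finally, the documents name no visit for the ANOVA and do not state that incomplete cases are deleted. Deletion is the usual behaviour of the named methods, and nothing in the plan provides an alternative.

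**Conclusion.** The gap is real and moderate. The plan has no analysis that uses the week-6 data of people who miss week 12, and it leaves its only three-visit method optional. The possible between-arm bias runs from about 0 with equal dropout to about 0.07 to 0.11 SD (baseline-adjusted) or 0.11 to 0.16 SD (unadjusted change) at 20% versus 40%, in either direction. These sizes rest on assumed correlations, dropout splits and a dropout mechanism tied to week-6 response. They show what could happen and do not predict this trial's result. The case for changing the plan is that a better method is available for the same data at almost no cost, and that it fixes the between-arm method before results are known.

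**What to change.** Replace the optional repeated measures sentence with a prespecified between-arm analysis for the continuous outcomes, for example:

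*The between-arm analysis is a linear mixed model on the week-6 and week-12 values, with arm, visit, arm by visit, baseline and baseline by visit, an unstructured covariance and Kenward-Roger degrees of freedom. It includes every randomised participant with at least one follow-up value. The main estimates are the 12-week contrasts of NMES+ against control and NMES+FES against control.*

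State how the Bonferroni correction applies to these contrasts and what role the Kruskal Wallis test keeps.

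The cost is wording and standard software, with no added visit, measurement or participant. With two follow-up visits the covariance has only three parameters, which is feasible with 45 people. There are two limits. The model assumes that data are missing at random given the observed values, and it does not recover people who leave before week 6. A simple sensitivity analysis should therefore accompany it, such as imputing the missing week-12 values with a stated range of less favourable shifts by arm, including for people with no follow-up. Report dropout by arm, timing and reason.
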